Urethral bladder catheterization carries a 6 to 12 percent of contamination rate. In regard clean catch urine method 16 to 63 percent of the contamination rate [2].

As outlined in the guideline in National Institute for Health and Care Excellence (NICE) guideline, to use clean catch urine wherever possible in pediatric patients below 16 years old. And to reserve bladder catheterization and suprapubic aspiration when noninvasive methods are not possible or practical [13].

Herreros et al. demonstrated a safe and noninvasive technique to collect midstream clean-catch urine in infants. It was based on bladder stimulation and paravertebral lumbar massage [14]. This technique yielded accurate and low contamination rates for infants below 90 days old. Moreover, the success rate was 86.3 percent, while the contamination rate was 5 percent. Nilgun et al. emphasized the safety and efficacy of the same stimulation technique in a neonatal intensive care unit setting. The median time to collect urine was 64 seconds. The success rate is 90 percent. However, Labrosse et al. showed a lower success rate reaching 61 percent, possibly due to patients with a low oral intake that were not excluded from the study [6,15].

In the effort to reduce bladder catheterization in children, different techniques were introduced in the previous literature to improve the clean catch urine success rate as well as the contamination rate [6,14,15,16]. Bladder and lumbar paravertebral massage maneuvers as described by Herreros et al are a safe, time-saving technique that needs to be studied further.

In our setting, the recommendations from international guidelines are being followed. For non-toilet trained children suspected to have UTI, initial urine specimen for urine dipstick is collected by sterile bag or bladder catheterization. If the result of the urine dipstick came positive, then urine culture is obtained via bladder catheterization, if the initial specimen collected by the sterile bag. In addition, we lack the statistics of urine culture contamination in our laboratories.

The main aim of this study is to introduce clean catch urine (bladder massage technique) to our setting, and to compare its feasibility with the bladder catheterization which is the standard practice.

4. Objectives and hypothesis of the study:

Primary outcome:

To compare the contamination rates between the two method and parent satisfaction.

Secondary outcome:

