To compare procedure duration in both methods. And pain score (using neonatal infant pain scale)

Study hypothesis

- The contamination rate of clean catch urine sampling is similar to the bladder catheterization.
- Less painful as it is less invasive.

5. Feasibility of the study

It is a multicentered study which enrolls pediatric patients who need urine collection according to the mentioned inclusion criteria. Notably, urinary tract infection (UTI) is a very common presentation in this age group, and it should be considered in almost all pediatric patients with fever with no clear source of infection. All the previously mentioned points can assure that the targeted sample size can be achieved within the designated timeline.

6. Research Design and Methods

Study design:

This pilot study will be conducted as randomized controlled trial.

Characteristics of study area and target population:

Study will be conducted in a tertiary hospital, pediatric emergency, and pediatric ward. Target population are pediatric patients aged between 0 to 6 months.

Primary and secondary endpoints:

Primary endpoints: Urine culture contamination rate and parental satisfaction

Secondary endpoints: Pain score (utilizing Neonatal Infant Pain Scale) and duration of the procedures.

Selection and withdrawal of subjects:

All infants younger than 6 months of age, who require urine sample as part fever work-up in emergency department.

Any subject may be withdrawn from the study at any time for any reason and without penalty or prejudice.

Sampling and sample size:

A pilot study with 40 samples in each arm will be conducted since there is no prior information about contamination rates in our local setting.

7. Randomization

The study will utilize computerized block randomization technique to assign participants into experimental and control groups, with each block being randomized to ensure unbiased allocation. The randomization will occur in the emergency triage.

8. Study flow

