Patient will be assessed in triage and cases to be included in the study as per the inclusion criteria, after that patients will be randomized using computerized block randomization technique into two groups. Then, patients will be assigned to a bed, pulse oximetry to be applied, data collection sheet to be filled, confirm that infant had good feeding/ didn't pass urine over last 20 minutes and proper cleaning to be done. The next step will be, collecting urine sample according to randomization group. Group A patients (control group), urine to be collected by standardized catheterization technique while group B by standard CCU technique. Meanwhile, time of each procedure to be documented. Regarding group B , after collecting urine by CCU , we recommend to collect another sample by catheterization to guide the management and antibiotic choice. (Appendix: Study flow chart)

9. Study procedures

Clean catch urine (bladder massage technique) provided in the appendix.

10. Variable definitions and measurements

Data collection tools and methods: (provided in the appendix)

Data quality:

In each site there will be a focal point doctor, responsible for the site. Before conducting the study, we will do training sessions about the study and we will prepare a video teaching the physicians/ nurses the steps of urine collection of by clean catch technique. Individual meetings to be conducted with the focal point for each site to clarify their inquiry. We will use a research assistant for data collection to facilitate the process and to help monitoring the flow of the study protocol.

Data analysis: We will use Statistical Package for the Social Sciences (SPSS) applications version 25 for our analysis.

11. Ethical considerations

Already we have the ethical approval from the ministry of health of Oman (proposal ID: MoH/CSR/23/26368), all recommended changes were adjusted before starting the study. If any risk on patient safety noticed during our study, we will make sure to stop the study protocol. We are not anticipating any harm to patient as the technique our study introducing is less invasive and more comfortable to patients. For the patient group with CCU collection, we are recommending another sample of urine to be collected to guide the antibiotics choice as CCU contamination rate and accuracy will be studied by this paper.

12. Conflict of interest

No conflict of interest

13. Incentives

No incentives of any kind will be given to the participants.

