14. Results Dissemination

The study results will be disseminated through various channels to ensure wider reach and maximum impact. This includes local and international publication of the

study in peer-reviewed journals, as well as presentation of findings at relevant conferences and symposiums. Additionally, we plan to share the study outcomes with relevant stakeholders such as healthcare professionals, policymakers to ensure that the findings are effectively translated into practice and policy.

15. Management and monitoring of the research activities

Each focal point will be responsible for that hospital work flow. As each focal point will be in direct contact with the workers at the specific site. Daily monitor to be done to check the new enrolled cases. The other researchers to follow the whole workflow weakly by contact the assigned focal point.

16. Limitations and difficulties of the study:

1. Constrained timeframe for research due to residency program obligations
2. Ensuring an adequate sample size

17. Rationale for subject selection and recruitment.

This is a randomized control study, aiming to study the feasibility and contamination rate of urine collected by clean catch technique comparing to catheterization technique. The population enrolled in this study, pediatric patients, that will benefit of introducing clean catch technique. This is a population who cannot give urine sample for laboratory testing without catheterization which is a painful procedure. The clean catch technique will be of much help for this age group as it is painless and less invasive technique. Therefore, it seems highly beneficial to study the contamination rate of CCU collection in order to introduce it in local guidelines to replace the current use of catheterization.

18. Statistical analysis:

For data entry purposes Microsoft Excel software will be used and for the data analysis IBM SPSS statistics will be used. Normally distributed continuous data will be analyzed using student T test, if abnormal MANN-WHITNEY test will be used. For categorical comparisons CHI-square test will be applied. P-value of less than 0.05% will be considered as statistical significance.

19. Criteria for terminating the study.

A subject who is included in the study, and failed urine collection by CCU , will be removed from study and counted as CCU collection failure. After that to be managed by in-charged doctor as per the treating doctor plan.

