- I have read the foregoing information, or it has been read to me. I have had the opportunity to ask questions about it.
- Any questions that I asked, they have been answered to my satisfaction. I consent voluntarily to participate as a participant in this research.

Authorized to consent name:

Relationship to the patient:

Signature date:

Researcher/Doctor:

Clean catch urine technique

Clean catch urine (bladder massage technique)

- Two people (trained nurses and/or physicians) were needed to perform the procedure, and a third to measure the time taken. This technique involves a combination of fluid intake and non-invasive bladder stimulation maneuvers .
- To provide breast-feeding or formula intake appropriate to the age and weight of the newborn. In babies fed infant formula, 10 ml was provided on the first day of life, increasing to 10ml per day during the first week. From the second week onwards, 25 ml/kg were administered before the onset of stimulation .
- Twenty-five minutes after feeding, the infant's genitals were cleaned thoroughly with warm water and soap and dried with sterile gauze .
- A sterile collector was placed near the baby to avoid losing urine samples.
- Hold the baby under their armpits with their legs dangling. One examiner then starts bladder stimulation which consists of a gentle tapping in the suprapubic area at a frequency of 100 taps or blows per minute for 30 seconds .
- Stimulation of the lumbar paravertebral zone in the lower back with a light circular massage for 30 s. Both stimulation maneuvers are repeated until micturition starts, and a midstream urine sample can be caught in a sterile collector.
- Success is defined as the collection of a sample within 5 min of starting the stimulation maneuvers.

Definitions for UTI, contamination, and insignificant growth

Urine culture results			
Definition	Urinalysis result	Organism(s) Cultured	Colony Threshold ^a
No growth	Negative	No growth	No growth
UTI	Positive ^b	1 Uropathogen ^c	≥100,000 CFU/mL
	Positive	1 Uropathogen	10,000–100,000 CFU/mL ^d
Contaminated	Negative	1 Non-uropathogen	≥100,000 CFU/mL
	Negative	≥2 Organisms (≥1 non-uropathogen)	Any colony count
	Negative	Mixed bacterial flora ^e	≥100,000 CFU/mL
Insignificant Growth	Positive or negative	1 Non-uropathogen	≤10,000 CFU/mL
	Negative	1 Non-uropathogen	≤100,000 CFU/mL

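### Removing failed clean-catch infants, with no matching rule for catheterization, tilts the duration comparison towards clean catch

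*Protocol*

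**What the plan says.** Section 6 of the Protocol lists duration as an endpoint: "Secondary endpoints: Pain score (utilizing Neonatal Infant Pain Scale) and duration of the procedures". Section 8 asks for it to be recorded in both arms ("Meanwhile, time of each procedure to be documented"), and the data collection sheet has a duration field in minutes. Section 18 gives the test: "Normally distributed continuous data will be analyzed using student T test, if abnormal MANN-WHITNEY test will be used".

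Two further statements decide whose times enter that test. The appendix on the clean-catch technique sets the only success criterion: "Success is defined as the collection of a sample within 5 min of starting the stimulation maneuvers". Section 19 says that an infant who "failed urine collection by CCU , will be removed from study and counted as CCU collection failure", after which the treating doctor takes over.

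For catheterization, Section 8 refers only to a standardized technique. The visible text gives no time limit, attempt limit, failure definition or removal rule. No section says when the clock starts or stops. The appendix also says "Both stimulation maneuvers are repeated until micturition starts" and does not say that stimulation ends at 5 min. The study flow chart is not reproduced in the text available, so it may settle some of this.

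**The concern.** Removal depends on the outcome being compared. If failure is read as the complement of success, the infants removed are exactly those with the longest stimulation times. This happens in one arm only, so truncated clean-catch times are compared with untruncated catheterization times. The direction is fixed: clean catch looks faster than it is.

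Section 22 anticipates that clean catch will prove more feasible, and Section 17 looks to its replacing catheterization in local guidelines. A reader will take collection time as part of that case. If removal also means that no time or outcome is written down for these infants, a later analysis plan can do little to bring them back.

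**Working it through.** The Protocol gives no figure for this point, and its 40 per arm is a pilot number without a power calculation. There is nothing to reproduce, so the calculations below only illustrate size.

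**Inputs**
- 40 infants per arm (Section 6).
- Clean-catch success rate s = 90%, 86.3% or 61%, from the studies cited in Section 3. Assumption: these are 5-minute rates.
- Two-sided significance level 0.05. This is assumed; Section 18 prints 0.05%.

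**1. Infants lost, 40 × (1 − s)**
- s = 0.90: 40 × 0.10 = 4
- s = 0.863: 40 × 0.137 = 5.5 (35 successes leave 5 failures)
- s = 0.61: 40 × 0.39 = 15.6

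**2. Shift in the pairwise comparison.** Suppose the methods are truly even over all randomised infants: clean catch is faster in 50% of pairs, with failures tied at the longest rank. Let c be the share of catheterizations that take over 5 min or fail. Clean-catch failures contribute (1 − s) × c/2 to the 0.5, so among retained infants the share is

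(0.5 − (1 − s) × c/2) / s

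| s | c = 0 | c = 0.25 | c = 0.5 |
|---|---|---|---|
| 0.90 | 0.5/0.90 = 55.6% | 0.4875/0.90 = 54.2% | 0.475/0.90 = 52.8% |
| 0.863 | 0.5/0.863 = 57.9% | 0.4829/0.863 = 56.0% | 0.4658/0.863 = 54.0% |
| 0.61 | 0.5/0.61 = 82.0% | 0.4513/0.61 = 74.0% | 0.4025/0.61 = 66.0% |

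This step does not assume equal time distributions. If they are equal, c = 1 − s and the formula reduces to 1 − s/2, giving 55.0%, 56.9% and 69.5%.

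**3. Effect on the test.** These are simulations with 40 per arm, the same time distribution in both arms, clean-catch failures removed and a two-sided Mann-Whitney test at 0.05. Times are exponential with 5 min placed at quantile s.

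| Setting | s = 0.90 | s = 0.863 | s = 0.61 |
|---|---|---|---|
| Clock from stimulation (20,000 runs) | 11.0% | 16.9% | 77.2% |
| Preparation time added, SD equal to the voiding-time SD (5,000 runs) | 9.2% | 13.4% | 37.9% |
| Preparation time added, SD twice the voiding-time SD (5,000 runs) | 7.4% | 8.5% | 16.5% |
| Failures and times over 5 min kept, tied longest, common clock (20,000 runs) | 4.9% | 4.9% | 5.0% |

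The result does not hinge on the exponential shape. Lognormal times with log-SD 0.8, 1.0 and 1.2 (4,000 runs each) give 11.2% to 11.7%, 16.6% to 17.6% and 76.7% to 78.1%. Almost all of these rejections favour clean catch. Keeping failures with the same 5-minute cap in both arms gives 4.6% to 5.3%.

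For scale in minutes, at log-SD 1.0 the clean-catch median among successes against all attempts is 1.22 against 1.39 (s = 0.90) and 1.41 against 1.68 (s = 0.863).

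**4. Weight of the 61% case.** Section 3 explains that rate as "possibly due to patients with a low oral intake that were not excluded from the study". Here Section 8 requires staff to check feeding first ("data collection sheet to be filled, confirm that infant had good feeding"), so 61% is an outer case and not a planning value.

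**The case against.** The strongest reply is that Section 19 concerns ending participation and never says that a failed infant's time leaves the duration analysis. Analysis sets usually belong in the SAP, which is not shown. Section 8 asks for every procedure to be timed, and the appendix assigns a third person to measure time, so the data may well exist. Even a bare failure count is enough to rank those infants longest. This weakens the claim that the data would be lost, which holds only if removal stops recording. It does not remove the point: the plain meaning of removal from the study is exclusion, and a SAP that kept these infants would have to override a stated rule.

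The size is also open to challenge. At 86.3% to 90% success the pairwise shift is 2.8 to 7.9 points, about 0.4 to 1.2 null standard errors at this sample size (√(77 / (12 × 36 × 40)) = 6.7 points). Nothing in the Protocol suggests that voiding after massage and catheter insertion share one time distribution. Duration is a secondary endpoint in a pilot, and no hypothesis predicts faster collection. All this is fair and limits the importance of the point, but it does not alter the direction.

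Time among successes, shown beside a success rate, is a recognised description, and Section 3 cites results that way. It is acceptable as a description but not as a randomised comparison against an untruncated arm.

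Finally, a clock started at stimulation leaves out the feeding and 25-minute wait listed under the clean-catch technique. Counting that wait in one arm only could outweigh the bias described here. Section 8 applies the feeding check and cleaning to both arms, so a clock started after cleaning is common to both. The objection strengthens the case for defining the clock.

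**Conclusion.** The concern holds. Followed as written, the Protocol drops the slowest clean-catch attempts from a stated secondary comparison and has no counterpart for catheterization. The bias from this removal favours clean catch. At success rates of 86.3% to 90% it is modest but not negligible. The inflated rejection rates assume equal time distributions in the two arms, and how far they rise depends on the clock. If timing starts at stimulation, no analysed clean-catch time can exceed 5 min. If preparation is included, recorded times can be longer, but slow voiders are still lost selectively.

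The conclusion rests on reading failure as no sample within 5 min and removal as exclusion from the duration analysis. The sizes rest on treating the cited success rates as 5-minute rates. The flow chart, which could contain a stopping rule or a catheterization failure route, was not available. The change should be made before times are collected.

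**What to change.** **Section 19.** Replace removal with this rule: the infant stays in the randomised group, counts as a clean-catch failure, and has duration censored at 5 min from the start of stimulation. Care then passes to the treating doctor, as now.

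**Appendix.** Add three definitions:
1. Stimulation stops at 5 min.
2. One clock applies to both arms, for example after cleaning, from the start of stimulation or of catheter insertion, until urine is obtained.
3. A failed catheterization is defined, for example as no urine after a stated number of attempts.

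**Data collection sheet.** Add a yes/no field for whether a sample was obtained.

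**Analysis.** Compare duration over all randomised infants by Mann-Whitney, with failures and times over 5 min in either arm tied at the longest rank. Section 18 already sends non-normal data to this test; naming it for duration removes doubt. Time among successful collections can be shown beside it as a description.

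**Cost.** One changed sentence in Section 19, three short definitions, one data field and, if wanted, a clause in Section 18. Staff must use the same clock in both arms. Clean-catch duration will read longer than under the current rule, and the test will not distinguish differences beyond 5 min.

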Job Title:	MD, FRCPc, Fellow in ICU and Sports Medicine. Emergency medicine consultant.
Email:	[contact]
Phone	[name]
Co-investigator:	
Title and Name:	[name] [name]
Staff ID:	80828
Job Title:	Pediatric specialist, OMSB
Email:	[contact]
Phone	[name]

2. Summary:

Introduction: Urinary tract infections (UTIs) are a common source of infection in children, accounting for a significant proportion of visits every year. Diagnosing UTIs requires obtaining a urine specimen, which can be collected using four methods: invasive techniques, such as suprapubic aspiration and urethral bladder catheterization, and noninvasive techniques, such as sterile bag and clean catch. However, catheterization can be a painful and invasive procedure, particularly in young infants who are less cooperative, and sometimes tends to be rejected by parents.

Given the availability of alternative methods with comparable contamination rates, we aim to investigate the feasibility and contamination rate of clean catch urine compared to bladder catheterization, as well as secondary outcomes such as pain scores, parental satisfaction, and time required to collect urine for each technique.

Methods: To achieve this, we will conduct a randomized control trial in precontinent pediatric patients. A pilot study with 40 samples in each arm will be conducted since there is no prior information about contamination rates in our setting. A well-designed and labeled data collection sheets will be used for data collection, and the data will be entered using EPI-data software. Statistical analysis will be performed using IBM SPSS statistics.

Aim: The main aim of this study is to introduce clean catch urine (bladder massage technique) to our setting, and to compare its feasibility with the bladder catheterization which is the standard practice.

Patient Population: young infants from 0 to 6 months of age

Intervention: There will be two groups:

1. Group A (Experimental group): Urine samples will be collected using the clean catch urine method (bladder massage technique).
2. Group B (Control group): Urine samples will be collected using the standard bladder catheterization method.

Clinical Measurement: All collected urine samples will be labeled and sent to the laboratory. All results will be retrieved from the medical records. Direct measurement will be for the duration of the procedures in both experiment and

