^aUrine culture colony counts had the same thresholds regardless of the method used to obtain the urine specimen (ie, urethral catheterization or bladder massage).

^bUrinalysis indicative for UTI-labeled positive: positive leukocyte esterase test and/or nitrite test, in addition to evidence of pyuria with >10 white blood cells per microliter. Urinalysis results that do not meet criteria for positive are considered negative.

^cThe identified organism is considered a uropathogen based on clinical judgment of the provider caring for the patient.

^dFor this range, providers must consider the patient's clinical presentation and whether the urinalysis supports the diagnosis of a UTI.

^eNomenclature indicating growth of 3 or more organisms.

Study flow chart

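### For some cultures the contamination endpoint turns on the treating clinician's unstandardised organism label, and one culture result falls into two classes at once

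*Protocol*

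**What the plan says.** Protocol Section 6 lists the endpoints: "Primary endpoints: Urine culture contamination rate and parental satisfaction". Section 2 (Clinical Measurement) gives the source of the data: "All results will be retrieved from the medical records". The Appendix, under Definitions for UTI, contamination, and insignificant growth, holds the only definition of contamination in this document. It has three *Contaminated* rows, all with a negative urinalysis:

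- row 1: one non-uropathogen at or above 100,000 CFU/mL;
- row 2: "≥2 Organisms (≥1 non-uropathogen"), at any colony count;
- row 3: mixed bacterial flora at or above 100,000 CFU/mL, which footnote e explains as three or more organisms.

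The second *Insignificant Growth* row covers one non-uropathogen with a negative urinalysis at "≤100,000 CFU/mL".

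Footnote c gives the only rule for the organism label: the "identified organism is considered a uropathogen based on clinical judgment of the provider caring for the patient". Footnote b makes urinalysis two-valued, since anything not positive is negative. Sections 8 and 11 recommend a further catheter sample after clean catch, to guide treatment.

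**The concern.** A primary endpoint should give the same value whoever reads the laboratory report. Here two clinicians can read one report, label the organism differently, and so change whether the culture counts as contaminated. The Protocol describes no list, adjudication or masking for that label. In the clean-catch arm the clinician may also know the result of the second, catheter sample, which has no counterpart in the catheter arm. Section 6 justifies the pilot by the lack of local contamination figures, so a definition that others can reproduce is central to what the pilot is meant to supply.

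The cut-offs raise a smaller problem of the same kind: one result satisfies two classes, and only one of them counts towards the endpoint.

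**Working it through.** No stated figure has to be reproduced, because the point concerns classification rules. Each table row was treated as a rule and applied to culture results at 5,000, 10,000, 50,000, 100,000 and 200,000 CFU/mL, first with at least one organism called a non-uropathogen, then with all called uropathogens.

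| Urinalysis | Organisms | CFU/mL | At least one called non-uropathogen | All called uropathogens |
|---|---|---|---|---|
| Negative | one | 5,000 to 50,000 | Insignificant Growth | no class |
| Negative | one | 100,000 | Contaminated **and** Insignificant Growth | no class |
| Negative | one | 200,000 | Contaminated | no class |
| Negative | two | every count | Contaminated | no class |
| Negative | three or more | below 100,000 | Contaminated (row 2) | no class |
| Negative | three or more | 100,000 and above | Contaminated | Contaminated (row 3, if footnote e covers any growth of three or more) |
| Positive | any | every count | never Contaminated | never Contaminated |

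**Label.** For one organism above 100,000 with a negative urinalysis, changing only the label moves the culture between *Contaminated* and no class. For two organisms the same happens at every count, but the culture leaves *Contaminated* only if both are called uropathogens. Once one is a non-uropathogen, the other's label is irrelevant. The label has no effect on this endpoint when the urinalysis is positive, nor for mixed flora at or above 100,000.

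**Overlap.** Row 1 requires a count of at least 100,000, and the second *Insignificant Growth* row allows at most 100,000. Both hold at exactly 100,000 and nowhere else. The other overlaps (the two UTI rows at 100,000, the two *Insignificant Growth* rows up to 10,000) stay within one class and are harmless.

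**Size.** Section 6 plans 40 samples in each arm.

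- One culture: 1/40 = 2.5 percentage points of that arm's rate.
- For scale, Section 3 cites 6 to 12 percent contamination for catheterization and 16 to 63 percent for clean catch. Assuming these apply here, 40 × 0.06 = 2.4 to 40 × 0.12 = 4.8 contaminated catheter cultures are expected, and 40 × 0.16 = 6.4 to 40 × 0.63 = 25.2 clean-catch cultures. One relabelled culture weighs most where the expected number is small.
- Denominator, for comparison, assuming 4 contaminated of 40: 4/40 = 10.0%. Dropping one to five unclassified cultures gives 4/39 = 10.3% to 4/35 = 11.4%. Relabelling a single culture as contaminated gives 5/40 = 12.5%.

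**The case against.** The strongest reply is that the effect is narrow and the same rules apply to both arms. Footnote a says that "colony counts had the same thresholds regardless of the method used to obtain the urine specimen". That holds for the counts, but it does not govern the organism label. The marker for footnote c stands on a UTI row and on no *Contaminated* row. Still, it is the only rule given for the term, and a non-uropathogen is simply its complement. A statistical analysis plan that is not shown might add a list or masked reading, but the Protocol already fixes this definition, so the fault lies in stated text and is not a mere omission.

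Some stronger readings do not stand:

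- *Rows 2 and 3 conflict for three or more organisms below 100,000.* The rows are alternatives. A culture with at least one non-uropathogen meets row 2 at any count, and missing row 3 does not cancel that.
- *The rate cannot be computed because many results have no class.* A culture meets a *Contaminated* row or it does not, so the numerator is countable apart from the overlap at 100,000. What is open is whether unclassified cultures stay in the denominator. That is a clarification, with the smaller effect shown above.
- *The data collection sheet omits the label.* It shows no field for culture or urinalysis results either, since these come from the records, so this proves little.
- *Each culture weighs more than 2.5 points in the clean-catch arm, because under Section 19 a failed collection "will be removed from study and counted as CCU collection failure".* The sample size statement reads "A pilot study with 40 samples in each arm will be conducted", so it counts samples. A smaller denominator needs another reading of that figure.

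**Conclusion.** The point holds in two parts. First, for negative-urinalysis cultures with one organism at or above 100,000 CFU/mL, or with two organisms at any count, an unstandardised label decides a primary endpoint; at exactly 100,000 the overlap adds to the ambiguity. Three or more organisms below 100,000 behave like two. Second, the cut-offs put one non-uropathogen at exactly 100,000 CFU/mL into two classes. The second part is a slip at a single value; the first is the substantive one.

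The size is 2.5 points per relabelled culture, taking 40 samples per arm as written. The total effect cannot be given, because the documents do not say how often these results occur or how often clinicians would disagree. A reader might infer that the comparison is biased towards one method, since the clinician may know the method and, after clean catch, a second result. The documents show an opening for that, but neither a direction nor a difference between arms. The endpoint definition should be corrected before classification starts; the finding does not invalidate the design.

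**What to change.** For endpoint classification only, with clinical diagnosis and care left unchanged:

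1. Replace footnote c, for the endpoint, with a prespecified list of uropathogens. Apply it to the laboratory report without knowledge of the collection method or of the second catheter sample.
2. In the second *Insignificant Growth* row, change the limit from at most 100,000 to below 100,000 CFU/mL. A count of exactly 100,000 then belongs to *Contaminated* alone.
3. As a minor clarification, state that the three *Contaminated* rows are alternatives, so that meeting any one is enough. State also that a culture meeting none of them counts as not contaminated and stays in the denominator of all cultures obtained.

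The cost is one organism list, a few lines in the Appendix, and classification of about 2 × 40 = 80 reports by someone not told the method. No test and no patient is added. The downside is that the endpoint label may differ from the treating clinician's label for some cultures, so the two must be recorded separately.
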